6.7 Exploratory/other analysis

For each scale from the patient reported outcomes, the mean response for LAO and OO groups at each assessment point up to 24 months will be presented graphically, with an indication of the number of patients in each group contributing to the estimates. Differences in quality of life are not expected to persist following the post-surgical recovery period. Any observed differences subsequent to three months post-randomisation will be noted in this exploratory analysis.

The Bang Blinding Index will be presented for both LAO and OO groups separately to assess the success of patient blinding to allocation in the first week post-surgery.

7. PUBLICATION PLAN

Once all allocated patients have completed their three-month assessment (late 2019) a data extract will be prepared for analysis of the main peri- and post-surgical measures, including the primary outcome. The tables and figures for this paper are presented in the next section (Tables 1, 2, 3, 4, Supplementary Table 1, Figure 1).

Once all allocated patients have completed their 24-month assessment (autumn 2021) a further data extract will be prepared for analysis of the PROs, complications and survival over that longer period (Table A, Figures A, B, C, D, E, Supplementary Tables as detailed in the next section).

8. FIGURES AND TABLES FOR JOURNAL PUBLICATION OF PRIMARY ANALYSIS

The following are the intended figures and tables for the main journal publications of the ROMIO results. Numbered tables and figures will be presented in the initial paper, those indexed by letters will appear in the subsequent paper.

Table 1. Baseline Characteristics by allocated surgery

	OO (n=)	LAO (n=)
Male; n (%)		
Mean age (SD), n		
Mean BMI (SD), n		
Mean POSSUM physiological score (SD), n		
WHO performance status score, n (%)		
0		
1		
2		
Tumour histologic findings; n (%)		
Adenocarcinoma		
Squamous cell carcinoma		
Adenosquamous		
Other		
Location of tumour in oesophagus; n (%)		
Upper third		
Middle third		
Lower third / Siewert I		
Junctional tumour, Siewert II		
Junctional tumour, Siewert III		
Clinical tumour classification; n (%)		
cT1		
cT2		
cT3		
cT4a		
Clinical node classification; n (%)		
cN0		
cN1		
cN2		
Neoadjuvant treatment; n (%)		
Chemotherapy		
Chemoradiotherapy		
None		

Table 2. Post-surgical recovery of physical function by allocated surgery (primary analysis)

	OO (n=)	LAO (n=)
PRIMARY ANALYSIS – pooled estimate		
Pre-randomisation mean (SD) n		
Three-week post-surgery mean (SD) n		
Six-week post-surgery mean (SD) n		
Three-month post-randomisation mean (SD) n		
Treatment effect (95% confidence interval) p-value		
SENSITIVITY ANALYSES		
Adjusted for time from randomization to surgery		
Treatment effect (95% confidence interval)		
Missing outcome data imputed		
Treatment effect (95% confidence interval)		

Table 3. Complications in those participants undergoing allocated surgery. Counts are of patients, who may have experienced more than one complication of a given type

	OO (n=)	LAO (n=)	p-value
Clavien-Dindo Classification of Complications, n (%)			
Normal recovery			
Grade I/II			
Grade IIIa / Grade IIIb			
Grade IVa / Grade IVb			
Grade V (death of patient)			
Key post-operative complications within 31 days of surgery, n (%)			
Oesophagoenteric leak from anastomosis, staple line, or localised conduit necrosis			
Conduit necrosis/failure			
Chyle leak			
Pneumonia / chest infection			
Delayed gastric emptying			
GI bleeding requiring intervention or transfusion			
Acute abdominal wall dehiscence/hernia			
Acute diaphragmatic hernia			
Key post-operative complications between 31 and 90 days of surgery, n (%)			
Oesophagoenteric leak from anastomosis, staple line, or localised conduit necrosis			
Conduit necrosis/failure			
Chyle leak			
Pneumonia / chest infection			
Delayed gastric emptying			
GI bleeding requiring intervention or transfusion			
Acute abdominal wall dehiscence/hernia			
Further intervention, n (%)			
Reoperation during index hospitalisation			
Return to ITU/HDU during index hospitalisation			
Within three months of randomisation			

Table 4. Peri- and post-surgical measures

	OO (n=)	LAO (n=)	p-value
30-day post-operative mortality, n (%)			
90-day post-operative mortality, n (%)			
Median total hospital stay in days (Q1, Q3) ¹			
Median post-surgical hospital stay in days (Q1, Q3) ¹			
Median total lymph nodes retrieved (Q1, Q3) ¹			
Median lymph nodes with tumour (Q1, Q3) ¹			
Resection margins, n (%)²			
R0			
R1			
R2			
pStage, n (%)²			
0			
I or II			
III			
IV			
No residual tumour or lymph-node metastasis			
Median FEV₁, as a percentage of pre-surgery (Q1 Q3), n			
Three days post-surgery ¹			
Six days post-surgery ¹			
Median FVC, as a percentage of pre-surgery (Q1 Q3), n			
Three days post-surgery ¹			
Six days post-surgery ¹			
Median pain (Q1, Q3), n; 0 is no pain, 100 is worst possible pain.			
Three days post-surgery ¹			
Six days post-surgery ¹			

1. p-value based on Mann-Whitney U statistic. Note that Q1 and Q3 are the first and third quartiles

2. p-value based on ordered logistic regression

Supplementary Table 1. Post-surgery treatment complications in those undergoing their allocated surgery [specific complications will be detailed if they occur in one or more patients – those listed here are examples only]

	OO (n=)	LAO (n=)
Pulmonary complications, n (%)		
Respiratory failure requiring intubation		
Acute respiratory distress syndrome		
Cardiac complications, n (%)		
Dysrhythmia atrial requiring treatment		
Dysrhythmia ventricular requiring treatment		
Urological complications, n (%)		
Acute renal insufficiency		
Gastrointestinal complications, n (%)		
Anastomotic stricture requiring endoscopic intervention		
Thromboembolic complications, n (%)		
Pulmonary embolism		
Neurological / psychiatric complications, n (%)		
Other neurological injury		
Post-operative infections, n (%)		
Wound infection requiring opening wound or antibiotics		
Post-operative wound / diaphragm complications, n (%)		
Acute abdominal wall dehiscence / hernia		
Other post-operative complications, n (%)		
Multiple organ dysfunction syndrome		

Supplementary Table 2. Cohort stratified and pre-specified subgroup analyses

	OO (n=)	LAO (n=)
Main study cohort		
Pre-randomisation mean (SD) n		
Three-week post-surgery mean (SD) n		
Six-week post-surgery mean (SD) n		
Three-month post-randomisation mean (SD) n		
Treatment effect (95% confidence interval)		
Feasibility study cohort		
Pre-randomisation mean (SD) n		
Three-week post-surgery mean (SD) n		
Six-week post-surgery mean (SD) n		
Three-month post-randomisation mean (SD) n		
Treatment effect (95% confidence interval)		
Neoadjuvant treatment		
Treatment effect (95% confidence interval)		
No neoadjuvant treatment		
Treatment effect (95% confidence interval)		
	Interaction p-value:	
BMI at or above the median		
Treatment effect (95% confidence interval)		
BMI below the median		
Treatment effect (95% confidence interval)		
	Interaction p-value:	
POSSUM Physiology at or above the median		
Treatment effect (95% confidence interval)		
POSSUM Physiology below the median		
Treatment effect (95% confidence interval)		
	Interaction p-value:	

Figure 1: CONSORT Flow chart

[figure not shown]

Table A. Survival and recurrence-free survival

	OO (n=)	LAO (n=)
Survival over 24 months post-randomisation		
Person-years of follow-up per group over 24 months		
Number of events over 24 months		
Survival at 24 months (95% confidence interval)		
Survival over full follow-up period		
Total person-years of follow-up per group		
Number of events		
Hazard ratio (95% confidence interval) p-value		
Recurrence-free survival over 24 months post-randomisation		
Person-years of follow-up per group over 24 months		
Number of events over 24 months		
Survival at 24 months (95% confidence interval)		
Recurrence-free survival over full follow-up period		
Total person-years of follow-up per group		
Number of events		
Hazard ratio (95% confidence interval) p-value		

Figure A: Mean QLQ-C30 Function sub-scale scores over two years of follow-up in patients allocated to LAO and OO. High scores indicate good function

Figure B: Mean QLQ-C30 Symptom sub-scale scores over two years of follow-up in patients allocated to LAO and OO. High scores indicate severe symptoms

Figure C: Mean QLQ-OES18 Function and Symptom sub-scale scores over two years of follow-up in patients allocated to LAO and OO. A high score indicates good swallowing function, and high symptom burden on the other measures

Figure D: Mean MFI-20 sub-scale scores over two years of follow-up in patients allocated to LAO and OO. High scores indicate greater fatigue

Figure E: Kaplan-Meier plot of (a) survival (b) recurrence-free survival in patients allocated to LAO and OO

Supplementary Tables: will give the numeric estimates of the means (standard deviations) for the PRO measures. An example table is given here to show the structure.

	OO (n=)	LAO (n=)
	Mean (SD) n	Mean (SD) n
QLQ-C30 Physical Function		
Pre-randomisation		
6-day post-surgery		
3-week post-surgery		
6-week post-surgery		
3-month post-randomisation		
6-month post-randomisation		
12-month post-randomisation		
18-month post-randomisation		
24-month post-randomisation		
QLQ-C30 Role Function		
Pre-randomisation		
6-day post-surgery		
3-week post-surgery		
6-week post-surgery		
3-month post-randomisation		
6-month post-randomisation		
12-month post-randomisation		
18-month post-randomisation		
24-month post-randomisation		

Supplementary Table X. Complications between three months and two years post-randomisation in those undergoing their allocated surgery [specific complications will be detailed if they occur in one or more patients – those listed here are examples only]

	OO (n=)	LAO (n=)
Other pulmonary complications, n (%)		
Respiratory failure requiring intubation		
Acute respiratory distress syndrome		
Cardiac complications, n (%)		
Dysrhythmia atrial requiring treatment		
Dysrhythmia ventricular requiring treatment		
Urological complications, n (%)		
Acute renal insufficiency		
Other gastrointestinal complications, n (%)		
Anastomotic stricture requiring endoscopic intervention		
Thromboembolic complications, n (%)		
Pulmonary embolism		
Neurological / psychiatric complications, n (%)		
Other neurological injury		
Post-operative infections, n (%)		
Wound infection requiring opening wound or antibiotics		
Post-operative wound / diaphragm complications, n (%)		
Acute abdominal wall dehiscence / hernia		
Other post-operative complications, n (%)		
Multiple organ dysfunction syndrome		

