3. GENERAL ANALYSIS CONSIDERATIONS

3.1 Analysis populations

Each of the following will include participants of the feasibility and main trials, according to the availability of data.

The primary effectiveness analysis will include data from the **“full analysis set”**; all randomised participants **in the groups to which they were allocated** (i.e. according to the intention-to-treat principle) who provide at least one of the three post-treatment assessments of physical function contributing to the primary outcome.

The **“safety set”** will include all randomised participants for whom there was an attempt to complete a study procedure (OO or LAO). This does not include patients for whom curative surgery did not proceed (e.g. due to the discovery of more advanced disease). The safety set does include participants who underwent a study procedure which was not that allocated, and participants who needed to convert from LAO to OO due to clinical reasons. This is the analysis population that will be used in the reporting of complications and adverse events. The groups to be compared will be defined by the study procedure **first initiated**, e.g. participants will be retained in the LAO group, even if they subsequently needed to convert to OO.

The **“per protocol set”** will include all randomised participants, **in their allocated groups**, for whom the allocated surgery was completed. Analyses of blinding, and surgical quality will use data from these participants.

Within the above three sets, about 120 feasibility phase patients, allocated to OO or LAO and with the necessary data, will be distinguished from those patients allocated to OO and LAO in the main study. In general, estimates of effectiveness will be stratified by feasibility and main study, and presented with a third pooled estimate using data from the two study phases.

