6.2 Summary of primary and secondary outcomes

For patients in the full analysis set, the number of patients providing data, mean, and standard deviation will be presented, by allocated group, for the time points used in the analysis of the primary outcome: baseline, three and six-weeks post-surgery, and three months post-randomisation. The primary outcome is based on the physical function scale of the QLQ-C30, a continuous measure with high scores indicating better physical function.

With regards to secondary outcomes, the same statistics will be presented for other scales derived from patient reported outcomes:

For function scales derived from the QLQ C-30 (role, emotional, cognitive, social), and global health status, high scores indicate high functioning / good quality of life.

For symptom scales derived from the QLQ C-30 (fatigue, nausea and vomiting, pain, dyspnoea, insomnia, appetite loss, constipation, diarrhoea, financial difficulties), high scores indicate greater symptom burden.

For the function scale derived from the QLQ-OES18 (dysphagia), a high score indicates good functioning.

For the symptom scales and items derived from the QLQ-OES18 (eating, reflux, pain, trouble swallowing saliva, choked when swallowing, dry mouth, trouble with taste, trouble with coughing, trouble talking), a high score indicates a high symptom burden.

For the five scales derived from the MFI-20 (general fatigue, physical fatigue, reduced activity, reduced motivation, mental fatigue) a high score indicates greater fatigue.

For the full analysis set, the occurrence of deaths, and of disease recurrence over a two-year follow-up period will each be presented for the LAO and OO groups as a Kaplan-Meier survival curves. Point estimates from these survival curves will be presented at 30 days and 90 days to allow comparison with National Audit Data.

For the safety set, the occurrence for each patient of one or more complications in each of the following key categories, both up to hospital discharge, and separately for the remainder of the 24-month follow-up, will be tabulated for the LAO and OO groups: oesophagoenteric leak and conduit necrosis/failure (patients experiencing each and both of these will be reported), chyle leak, pneumonia, gastrointestinal bleeding requiring intervention or transfusion. The number of patients requiring readmission to ITU/HDU will also be presented.

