6.4.4 Surgical complications during hospital stay

Using the safety set, the null hypothesis of true equality in the proportion of patients experiencing one or more episodes of each of the key complications (oesophagoenteric leak, conduit failure, chyle leak, pneumonia, GI bleeding requiring intervention) will be tested using a chi-square test.

For each patient the most severe impact of any complications during their initial hospital stay will be categorised using the Clavien-Dindo system(2), patients in the LAO and OO groups being compared using ordered logistic regression.

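### The SAP text and its table shells put complications on different populations and in different time windows, so counts and p-values depend on which is followed

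*SAP*

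**What the plan says.** **Population, in the text.** SAP section 3.1 says of the safety set: "This is the analysis population that will be used in the reporting of complications and adverse events". On grouping it says "The groups to be compared will be defined by the study procedure" first initiated, so a patient converted from LAO to open surgery stays in LAO. It adds: "The safety set does include participants who underwent a study procedure which was not that allocated". Sections 6.2 and 6.4.4 name the safety set again for the complication summaries and tests.

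**Population, in the tables.** In section 8, Table 3 is titled "Complications in those participants undergoing allocated surgery". Supplementary Table 1 has the same restriction, and Supplementary Table X is titled "Complications between three months and two years post-randomisation in those undergoing their allocated surgery".

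**Window, in the text.** Section 6.2 tabulates key complications "both up to hospital discharge, and separately for the remainder of the 24-month follow-up". Section 6.4.4, whose heading limits it to the hospital stay, is the only place that specifies tests: a chi-square test for each key complication, and ordered logistic regression for the Clavien-Dindo grade, taken as the "most severe impact of any complications during their initial hospital stay".

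**Window, in the tables.** Table 3 has a p-value column. Its first block of complication rows is headed "Key post-operative complications within 31 days of surgery, n" (%), and its second covers 31 to 90 days after surgery. Supplementary Table X runs from three months after randomisation.

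**The concern.** Complications are the first two secondary outcomes listed in section 2.10.2, and section 7 places Table 3 in the first paper. Section 1 says the plan should let someone else carry out the analysis. On this point it does not: an analyst working from sections 3.1 and 6.4.4 and one working from the Table 3 shell would use different patients and count events over different periods. The 31 to 90 day rows have a p-value column but no matching test in the text, and the in-hospital tests of key complications have no rows in Table 3. An unresolved choice of this kind can be made after the results by arm are known.

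The choice is also more than clerical. Discharge is not a neutral end to an observation period, because section 6.4.7 compares length of stay between the arms. If one arm goes home sooner, its patients are observed for fewer days in a test that stops at discharge.

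**Working it through.** The SAP states no complication rate, conversion rate or discharge time, so there is no figure to reproduce. (The 182 per group in section 2.7 concerns physical function only.) The conflict itself is settled by comparison:

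| Item | Sections 3.1, 6.2, 6.4.4 | Section 8 tables |
|---|---|---|
| Patients | Safety set | Those having their allocated surgery |
| Crossovers | Kept, under the procedure first started | Excluded |
| LAO-to-OO converters | Kept in LAO | Excluded on the likely reading |
| Period for p-values | Hospital stay (6.4.4) | Within 31 days; 31 to 90 days after surgery |
| Complications listed | Leak, conduit failure, chyle leak, pneumonia, GI bleeding | These plus delayed gastric emptying, abdominal wall dehiscence or hernia, diaphragmatic hernia |

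Three smaller mismatches follow from the same texts.
- Day 31 belongs to both Table 3 periods.
- Section 6.4.4 counts GI bleeding needing intervention, while section 6.2 and Table 3 also admit transfusion.
- Supplementary Table X uses a different clock. If surgery is on day 14 (section 2.6 aims for two weeks) and three months is taken as 91 days, Table X starts at post-operative day 91 − 14 = 77. Days 77 to 90 then fall in both tables.

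**Denominators.** Section 2.7 allows for 5% of LAO-allocated patients having open surgery: 0.05 × 203 ≈ 10. It does not say whether these are crossovers or conversions. Suppose everyone has surgery and nobody crosses from OO to LAO.
- If the 10 are crossovers, the safety set is 193 LAO and 213 OO; the Table 3 title gives 193 and 203.
- If the 10 are conversions, the safety set is 203 and 203; the Table 3 title, read as excluding converters, gives 193 and 203.

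**Dropping converters (all rates assumed).** With overall LAO rate r, converted share c and converters' rate q, the rate after exclusion is (r − c·q)/(1 − c). Take r = 30% and c = 5%:
- q = 50%: (0.30 − 0.025)/0.95 = 28.9%, a fall of 1.1 points
- q = 60%: 28.4%, a fall of 1.6
- q = 80%: 27.4%, a fall of 2.6
- q = 30%: no change
- q = 10%: 31.1%, a rise of 1.1

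With q from 50% to 80% and c from 2% to 10%, the fall is 0.4 to 5.6 points.

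**Dropping crossovers (20-point excess risk assumed).** Ten LAO-allocated patients started as OO count in OO in the safety set. Removing them lowers the OO rate by 10/213 × 20 = 0.9 points and leaves the LAO rate unchanged, which works against LAO.

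**Closing at discharge (all inputs assumed).** Give both arms the same 30% risk with exponential onset of mean m days, so the proportion counted by day t is 0.30 × (1 − exp(−t/m)).
- m = 5, discharge day 14 (OO) and 13 (LAO): 28.2% against 27.8%, a spurious gap of 0.4 points
- m = 10, discharge day 12 (OO) and 9 (LAO): 21.0% against 17.8%, a spurious gap of 3.2 points

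Other combinations of m from 5 to 10 days, OO discharge at day 12 or 14 and LAO discharge 1 to 3 days sooner lie between these. A 31-day window gives identical rates in the two arms. The sketch treats discharge as unrelated to complications, although a complication may itself prolong the stay.

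**The case against.** The strongest reply is that the population is already fixed. Three text sections agree on the safety set, section 3.1 says outright that it serves for complications, and section 8 holds empty shells. On that view the titles are slips. Much of this stands, and it is why the tables should be brought to the text and not the reverse. But three tables carry the same restriction, and the reply does nothing for the windows, where no statement says which period the p-values belong to.

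A second reply is that a patient whose LAO was begun and then converted has arguably undergone LAO; the titles say neither completed nor per protocol. That is fair. Exclusion of converters is the likely reading, because section 5.5 treats conversion as moving away from the allocated surgery and outside the per protocol set, but it is an inference. Exclusion of crossovers is not.

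A reader might go further and infer three things that the SAP does not support.
- *That both discrepancies make LAO look safer.* Dropping converters does so only if their risk is above average. Stopping at discharge does so only if LAO patients leave earlier. Dropping LAO-to-OO crossovers with above-average risk acts in the opposite direction, so the 5% in section 2.7 cannot be used as the size of a bias in favour of LAO.
- *That events after discharge go unreported.* Section 6.2 tabulates them for the rest of the 24 months; only the tests in 6.4.4 stop at discharge.
- *That the Clavien-Dindo grade has the same fault.* Sections 2.10.2 and 6.4.4 both tie it to the hospital stay, and its block in Table 3 states no other period. Moving it to fixed windows would be a preference.

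The overlap between Table 3 and Supplementary Table X is also minor: Table X has no p-values, belongs to the later paper, and shares only one of its example rows with Table 3.

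**Conclusion.** The point holds as an inconsistency that affects reported results. Text and tables disagree on who is counted, over what period and for which complications, and the SAP does not say which period the p-values describe. Possible shifts of a few tenths of a point to several points are illustrations on assumed rates, onset times and discharge days. They show that the choice can matter, not how much it will matter here or in which direction. The primary outcome, sample size and power are untouched. The matter should be settled before complication counts by arm are examined for the paper.

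**What to change.** - Retitle Table 3 and Supplementary Tables 1 and X for the safety set, grouped by procedure first initiated.
- In sections 6.2 and 6.4.4, test the key complications in fixed, non-overlapping periods from the date of surgery, for example days 0–30 and 31–90, and give Table 3 the same limits. Keep counts up to discharge as description.
- Use one list of key complications, with one definition of GI bleeding, in 6.2, 6.4.4 and Table 3.
- Start Supplementary Table X where Table 3 ends, counted from surgery.
- Leave the Clavien-Dindo grade defined up to discharge and label its block in Table 3 accordingly.

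The cost is revised SAP wording and table shells, recorded in the table of changes that section 5.6 requires. Table 3's existing rows already need dated complications, so the two fixed periods call for no new data.
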